**Variables:**

- *Exposures:* Exposure to the COMIRNATY 2023-2024 Formula will be defined by the presence of National Drug Codes (NDC) on pharmacy claims or Healthcare Common Procedure Coding System (HCPCS) codes on medical claims.
- *Outcomes:* The pre-specified safety outcomes of interest include the following: acute disseminated encephalomyelitis (ADEM), anaphylaxis, Bell's palsy, cerebral venous sinus thrombosis (CVST), convulsions/seizures (non-febrile), encephalomyelitis, glomerulonephritis, Guillain-Barré syndrome, herpes zoster, immune-mediated myositis, immune thrombocytopenia, Kawasaki disease, multi inflammatory syndrome (in children and adults), multiple sclerosis (MS), myocardial infarction (MI), myocarditis/pericarditis, pulmonary embolism (PE), hemorrhagic stroke, ischemic stroke, and transverse myelitis. Study outcomes will be identified through claims indicators using published validated claims-based algorithms with high performance when available.
- *Covariates:* Baseline covariates will include information related to patient demographics, comorbidities, COVID-19 vaccination, healthcare utilization, and medication history. Additional baseline covariates will be identified on an empiric basis by examining the most frequently occurring diagnoses, drugs dispensed, and procedures performed among individuals with and without COMIRNATY 2023-2024 Formula exposure. Demographic

090177e1a5be86fe\Approved\Approved On: 19-Mar-2026 15:57 (GMT)

attributes will be determined on the vaccination/cohort entry date, while other factors will be assessed in the one year prior to the vaccination date or cohort entry date.

**Data sources:** The patients included in this study will be drawn from the Optum pre-adjudicated claims database for the interim report and from the Optum Research Database (ORD) for the final reporting. The pre-adjudicated medical claims, which are supplemented with adjudicated pharmacy claims and health plan enrollment information, encompass hospital and physician claims that are submitted and processed daily from a large US commercial health plan. The individuals included in the pre-adjudicated medical claims database are fully insured by the health plan, which provides reimbursement of medical and pharmacy services regardless of site of care, and individuals are geographically diverse within the US. The ORD is a proprietary research database containing eligibility and adjudicated pharmacy and medical claims data from a large US health plan affiliated with Optum. In 2021, data were available for approximately 12.6 million individuals with medical and pharmacy coverage.

**Study size:** The sample size achieved will depend on the number of recipients of the COMIRNATY 2023-2024 Formula in the databases. All individuals who meet the study's eligibility criteria during the study period will be included.

**Data analysis:**

*Phase 1:* For the SCRI design, the observed incidence rates of the pre-specified safety outcomes of interest will be estimated in the risk window and the control window. Among individuals who experience an outcome of interest, an exact conditional Poisson regression model with the natural logarithm of the person-time as the offset will be used to calculate the rate ratio and corresponding 95% confidence interval (CI) of events occurring during the risk period relative to the control period. The results from the SCRI utilizing the Optum pre-adjudicated claims database will be presented in the interim report, while results utilizing the ORD will be presented in the final report.

*Phase 2:* In the cohort study, propensity score matched cohorts of COMIRNATY 2023-2024 Formula-vaccinated patients and comparator patients with no recorded dose of the COMIRNATY 2023-2024 Formula will be created. Following the application of outcome-specific exclusions, the incidence rate of each safety outcome will be estimated among the COMIRNATY 2023-2024 Formula-exposed group and its matched comparator group. The rate ratio will be estimated using unconditional Poisson regression that accounts for the matching process and for individuals who are included in both study cohorts. Secondary analyses will be conducted separately for various subsets of the matched comparator group, including comparators who received a non-COMIRNATY 2023-2024 COVID-19 vaccine on cohort entry, who received a non-COVID-19 vaccine on cohort entry, and who did not receive a vaccine on cohort entry by had another type of qualifying outpatient health encounter. Subgroup analyses will be conducted among individuals receiving concomitant non-COVID-19 vaccines; immunocompromised individuals; individuals with specific baseline comorbidities; individuals with prior SARS-CoV-2 infection; individuals with prior COVID-19 vaccination; pregnant women; individuals aged < 18 years; and individuals aged

≥ 65 years. Lastly, a descriptive analysis of the matched cohorts will focus specifically on outcomes related to pregnancy (spontaneous abortion, stillbirth, preterm birth, major congenital malformations and small for gestational age).

**Milestones:** Planned start of data collection is 15 January 2024. Planned completion date for the interim report is 30 June 2024. The planned end of data collection is 31 August 2025, and the planned completion date for the final report is 30 April 2026.

090177e1a5be86fe\Approved\Approved On: 19-Mar-2026 15:57 (GMT)

## 5. AMENDMENTS AND UPDATES

Version Identifier	Date	Amendment Type (substantial or administrative)	Protocol Section(s) Changed	Summary of Amendment(s)	Reason
3.0	18 March 2026	Administrative	4	Clarified the secondary and subgroup analyses in the abstract	Clarification between secondary and subgroup analyses
3.0	18 March 2026	Substantial	9.3.2.	Expands the circumstances where medical records may be retrieved to include analyses beyond safety signals in the primary SCRI analysis in the interim report	Provides operational flexibility to obtain medical records in the final report or in analyses besides the primary SCRI analysis if a safety signal is detected or if estimates are approaching the safety signal threshold
3.0	18 March 2026	Administrative	9.3.3.	Specified the form of each variable (categorical, continuous, binary)	Additional clarification on the model specification
3.0	18 March 2026	Administrative	9.3.3.	Clarified that other vaccinations are included in the empirical examination	Vaccinations are captured through NDC or CPT codes
3.0	18 March 2026	Administrative	9.7.2.1.	Specified the logistic regression model that will be used to estimate propensity scores, how calendar time will be included, and noted that scores will be matched to a maximum of 8 decimal places	Additional clarification on the model specification and details of propensity score matching
3.0	18 March 2026	Administrative	9.7.2.2.	Specified that the primary analysis accounts for both the matching ratio and individuals included in both study cohorts	Improved clarity of analytic methods
3.0	18 March 2026	Administrative	9.7.2.3.	Specified that the secondary analyses account for both the matching ratio and	Improved clarity of analytic methods

090177e1a5be86fe\Approved\Approved On: 19-Mar-2026 15:57 (GMT)

PFIZER CONFIDENTIAL

Version Identifier	Date	Amendment Type (substantial or administrative)	Protocol Section(s) Changed	Summary of Amendment(s)	Reason
				individuals included in both study cohorts	
3.0	18 March 2026	Administrative	9.7.2.4.	Specified that the subgroup analyses will include propensity score as a covariate in the model and will account for individuals included in both study cohorts	Improved clarity of analytic methods
3.0	18 March 2026	Administrative	9.9.	Added to the limitations the potential for residual confounding due to the use of a 1-year covariate period, not including prior COVID-19 vaccination in the propensity score model, and not accounting for other baseline vaccinations besides seasonal influenza and RSV vaccines.	Additional details to clarify the impact on potential confounding
2.0	29 August 2025	Administrative	4, 9.2	Corrected two typographical errors referring to the incorrect start of study accrual for the cohort analysis (corrected to 11 September 2023)	Typographical error in Version 1
2.0	29 August 2025	Substantial	4, 9.2.4, 9.3.3	Covariates will be assessed in the 1 year prior to cohort entry date as opposed to all available data	The 1-year lookback period is sufficient for capturing baseline covariates
2.0	29 August 2025	Administrative	6	Replaced references to 'EU PAS Register' with 'HMA-EMA Catalogues of RWD Studies'	Change in name of the publication registration catalogue
2.0	29 August 2025	Administrative	8	Changed the information about product approval to past tense	The information regarding the 2023-2024 Formula is no

090177e1a5be86fe\Approved\Approved On: 19-Mar-2026 15:57 (GMT)

PFIZER CONFIDENTIAL

Version Identifier	Date	Amendment Type (substantial or administrative)	Protocol Section(s) Changed	Summary of Amendment(s)	Reason
					longer present tense
2.0	29 August 2025	Administrative	9.1.2, 9.2.3, 9.7.2.1	Clarified details regarding propensity score matching in the cohort study analysis	Additional details provided for improved clarity
2.0	29 August 2025	Substantial	9.2.1.2, 9.2.2.1	Clarified that individuals receiving any COVID-19 vaccine (including prior COMIRNATY 2023-2024 Formula) would be excluded from the SCRI and cohort analyses	To ensure a proper washout period, excluding prior COMIRNATY 2023-2024 Formula is needed for individuals who may receive more than 1 dose
2.0	29 August 2025	Administrative	9.2.2.1	Corrected a typographical error referring to the incorrect study phase	Typographical error in Version 1
2.0	29 August 2025	Administrative	9.2.3, 9.2.5.2	Added details on the cohort entry date for the comparator cohort	Additional details provided for improved clarity
2.0	29 August 2025	Administrative	9.2.5.2	Specified that follow-up for the cohort study will end at one year following cohort entry (as mentioned in other sections) and clarified the end of follow-up criterion related to receipt of a subsequent COVID-19 vaccine	Additional details provided for improved clarity
2.0	29 August 2025	Administrative	Table 2	Corrected clean periods and vaccine risk windows for select outcomes	Typographical errors in Version 1
2.0	29 August 2025	Administrative	9.3.3	Clarified that prior COVID-19 vaccination will be descriptive only	Variable not included in the propensity score because doses during the 270 days prior to cohort entry are excluded

090177e1a5be86fe\Approved\Approved On: 19-Mar-2026 15:57 (GMT)

Version Identifier	Date	Amendment Type (substantial or administrative)	Protocol Section(s) Changed	Summary of Amendment(s)	Reason
2.0	29 August 2025	Administrative	9.3.3	Clarified that prior COVID-19 vaccination will be a binary variable for receipt of vaccine vs no receipt and will not be examined by year	Quantifying variable by doses prior to 2023-2024 is not possible now that the baseline period is limited to 1 year
2.0	29 August 2025	Administrative	9.3.3, 15.4.2.2	Clarified that the covariate of corticosteroids is restricted to oral routes	Additional details provided for improved clarity
2.0	29 August 2025	Administrative	9.3.3	Clarified the number of most frequently occurring codes that will be examined	Additional details provided for improved clarity
2.0	29 August 2025	Administrative	9.7.1.1	Clarified that the exact conditional Poisson regression model will be used among individuals who experience an outcome of interest in either the risk window or the control window (but not both)	Additional details provided for improved clarity
2.0	29 August 2025	Administrative	9.7.2.3	Changed a numbered list to a bulleted list	Formatting change
2.0	29 August 2025	Substantial	4, 9.7.2.4	Updated the subgroup analysis for individuals $\leq 18$ years of age to state that this will be done among individuals $< 18$ years of age	Revised to match the more commonly used definition for the pediatric population ( $< 18$ years)
2.0	29 August 2025	Administrative	9.7.2.4	Clarified that the prevalence of major congenital malformations will be evaluated among individuals whose pregnancy results in a live birth.	Additional details provided for improved clarity

090177e1a5be86fe\Approved\Approved On: 19-Mar-2026 15:57 (GMT)

090177e1a5be86fe\Approved\Approved On: 19-Mar-2026 15:57 (GMT)

PFIZER CONFIDENTIAL

*CT24-WI-GL02-RF02 7.0 Non-Interventional Study Protocol Template For Secondary Data Collection Study*

## 6. MILESTONES

Milestone	Planned Date
Final study protocol	31 March 2024
Registration in the HMA-EMA Catalogues of RWD	To be determined
Start of data collection a	15 January 2024
Interim report b	30 June 2024
End of data collection c, d	31 August 2025
Final study report d	30 April 2026

a For studies with secondary data collection, the start of data collection is defined as the planned date for starting data extraction for the purposes of the interim analysis.

b The milestone date was chosen to inform decision making for the next adapted vaccine before Fall 2024. To meet this milestone, the data extraction for the interim reporting will include data through 15 January 2024.

c For studies with secondary data collection, the end of data collection is defined as the planned date on which the analytical dataset will be first completely available; the analytic dataset is the minimum set of data required to perform the statistical analysis for the final reporting.

d The sponsor may extend the study period. This revision, if needed, will be communicated to the FDA as a protocol amendment. Details on this contingency plan are provided in [Section 9.2](#).

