#### **9.2.5. Follow-Up Period**

##### **9.2.5.1. SCRI**

In the SCRI analysis, follow-up for the risk period will begin upon (for the outcomes of anaphylaxis and convulsions/seizures) or one day after (for all other outcomes) receipt of the COMIRNATY 2023-2024 Formula ([Table 2](#)) and continue until the earliest of:

- Receipt of a COVID-19 vaccine other than the COMIRNATY 2023-2024 Formula;
- The end of the outcome-specific risk interval as defined in [Section 9.3.2](#);
- Disenrollment from the health plan, death, or the end of data collection.

After the outcome-specific pre-specified washout period following the risk interval, follow-up for the control period will begin and continue until the earliest of:

- Receipt of a COVID-19 vaccine other than the COMIRNATY 2023-2024 Formula;
- The end of the control period as defined in [Section 9.3.2](#);
- Disenrollment from the health plan, death, or the end of data collection.

Individuals will be followed for each safety outcome during both the risk and control periods, such that events observed during the risk period or washout period will not censor follow-up for the control period.

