### 9.3.2.1. Outcome-Specific Risk and Control Periods

The SCRI design ([Section 9.1.1](#)) requires that clean periods, risk intervals, washout periods, and control intervals be specified for every study outcome. The lengths of the clean periods and risk intervals are listed in [Table 2](#). The washout period for all outcomes will begin immediately after the end of the risk interval and continue for 30 days ([Akpandak et al., 2022](#)); the control period will follow the washout period and be equivalent in length to the risk interval. Interval lengths were determined based on prior vaccine literature, including COVID-19 vaccine studies conducted as part of the FDA’s Center for Biologics Evaluation and Research (CBER) Biologics Effectiveness and Safety (BEST) System ([Akpandak et al., 2022](#); [Barda et al., 2021](#); [CBER, 2021](#); [Joy et al., 2023](#); [Klein et al., 2021](#); [Liu et al., 2023](#); [Martin et al., 2021](#); [McCarthy et al., 2013](#); [Wack et al., 2021](#)).

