#### **9.6. Data Management**

All analyses will be conducted using Statistical Analysis System (SAS) version 9.4 (SAS Institute Inc., Cary, North Carolina) and SAS Enterprise Guide 6.1 or later. The data will be

---

 CPT copyright 2024 American Medical Association. All rights reserved.

extracted once per report. All reports will utilize the structured data only. The interim report will include summarized results from the Optum pre-adjudicated claims database described in [Section 9.4.1](#). The final report will include results summarized from the ORD as described in [Section 9.4.2](#). The characteristics of patients to be included in each data extract (e.g., required vaccine codes) and the specific timeframes of each data extract will reflect the study inclusion/exclusion criteria described in [Section 9.2](#), the baseline and follow-up periods in [Sections 9.2.4](#) and [9.2.5](#), and the study variables in [Section 9.3](#). All reports and deliverables will contain aggregated results only and will not identify individual patients, physicians, or facilities.

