## 9.9. Limitations of the Research Methods

The proposed project is based on analysis of automated medical and prescription claims, including pre-adjudicated (interim reporting) and fully adjudicated claims (final reporting).

For the interim report, the SCRI analysis will be based on automated and prospectively collected pre-adjudicated medical and adjudicated prescription claims. A strength of pre-adjudicated medical claims is the shorter lag time between the receipt of care and the appearance of the claim, while the accompanying limitation is that these pre-adjudicated claims may be subject to revision during the adjudication process. A limitation of the SCRI design may be its limited ability to assess chronic outcomes such as MS. Thus, the cohort analysis will be used as the primary analysis for chronic outcomes.

While adjudicated claims data are extremely valuable for the efficient and effective examination of healthcare outcomes, treatment patterns, healthcare resource utilization, and costs, all claims databases have certain inherent limitations because the claims are collected for the purpose of payment, not research. The presence of a diagnosis code on a medical

claim is not confirmation of disease, as the diagnosis code may be incorrectly coded or included as rule-out criteria rather than actual disease.

Another limitation of claims data relates to potential misclassification of exposure covariates. For instance, vaccines that are administered as part of a government program or an office-based or school-based vaccination clinic may not be captured in our database if insurance information was not provided during the vaccine encounter. This potential exposure misclassification is minimized in the self-controlled design in Phase 1; misclassification of exposure in Phase 2 would be expected to bias the results towards the null (CDC, 2023e). Furthermore, the presence of a claim for a filled prescription does not indicate that the medication was consumed or that it was taken as prescribed. Medications paid for out-of-pocket, as well as those not dispensed through a pharmacy, will not be observed in the claims data. Similarly, we may not have complete history of comorbidity or treatment for individuals due to switching in health plan insurer.

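### The interim SCRI sets its data cut-off and the planned start of its only extraction on the same day with no claims run-out, so under no vaccine effect any claim lag pushes the interim rate ratio above 1

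*Protocol*

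**What the plan says.** Section 6, footnote a: "the start of data collection is defined as the planned date for starting data extraction for the purposes of the interim analysis". The Milestones paragraph of the abstract gives that date: "Planned start of data collection is 15 January 2024". Footnote b then sets the last date of data: "To meet this milestone, the data extraction for the interim reporting will include data through 15 January 2024". Section 9.6 says that data are "extracted once per report".

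In Section 9.2.5.1, SCRI follow-up in either window ends at the window's end, at receipt of another COVID-19 vaccine, or at "Disenrollment from the health plan, death, or the end of data collection". Section 9.3.2.1 fixes a 30-day washout after the risk interval and adds that "the control period will follow the washout period and be equivalent in length to the risk interval". Section 9.7.1.1 fits an exact conditional Poisson model with log person-time as offset.

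Section 9.9 counts as a strength of pre-adjudicated claims "the shorter lag time between the receipt of care and the appearance of the claim". The weakness it names for these claims is later revision in adjudication; incomplete recent claims are not mentioned.

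**The concern.** A self-controlled design removes what is constant within a person. Claim completeness at a fixed extraction date is not constant: it falls as the service date approaches that date, and the control window is always the later of the two. The model compares recorded events per counted day. If the most recent days count in the denominator before their claims have arrived, the control rate is too low and the ratio too high with no vaccine effect at all. More events do not cure this; they only make the shifted estimate look more precise.

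The interim report was timed to inform decisions on the next adapted vaccine (Section 6, footnote b), and a signal in it is the one trigger for which Section 9.3.2 makes record retrieval mandatory.

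**Working it through.** **No plan figure to reproduce.** The protocol gives no event counts, lag or uptake figures. The dates below come from Table 2, the 30-day washout and the 15 January 2024 cut-off. The lag and uptake are assumptions.

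**Step 1: dates.** For a risk interval of Days 1 to L, the control window is Days L+31 to 2L+30.

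| Risk interval | Control window | Complete if vaccinated by | No control time if vaccinated after |
|---|---|---|---|
| Days 1–21 (myocarditis/pericarditis) | Days 52–72 | 4 Nov 2023 | 24 Nov 2023 |
| Days 1–28 (MI, PE, stroke) | Days 59–86 | 21 Oct 2023 | 17 Nov 2023 |
| Days 1–42 (Guillain-Barré syndrome, Bell's palsy) | Days 73–114 | 23 Sep 2023 | 3 Nov 2023 |

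For 42-day outcomes the first possible control day is 11 September + 73 days = 23 November 2023. All their control time therefore lies in the 54 days up to and including the cut-off.

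**Step 2: one person.** Let m be the median lag and F(x) = 1 − 2^(−x/m) the chance that a claim for care x days before extraction is present, with F(0) = 0. At constant incidence and true ratio 1, the apparent ratio is mean F over counted risk days divided by mean F over counted control days.

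Take a 42-day outcome, vaccination on 14 October 2023 and extraction on 15 January 2024. The risk window is 15 October to 25 November, 92 to 51 days before extraction. The control window starts on 26 December and is cut at 15 January: 21 days, aged 20 to 0 days.

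- m = 7: the sum of 2^(−k/7) for k = 0 to 20 is (1 − 2^(−3))/(1 − 2^(−1/7)) = 0.875/0.0943 = 9.28. Control completeness is 1 − 9.28/21 = 0.558; risk completeness is 0.998. Ratio 0.998/0.558 = 1.79.
- m = 3: the sum is 0.9922/0.2063 = 4.81. Control completeness is 1 − 4.81/21 = 0.771; risk completeness is 1.000. Ratio 1.30.
- m = 7 with a 60-day run-out: the control loss is multiplied by 2^(−60/7) = 0.0026, so completeness is about 0.999 and the ratio about 1.00.

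**Step 3: all vaccinees.** Sum the conditional Poisson score over vaccination dates from 11 September 2023 to 15 January 2024 and solve for θ:

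Σ w·[E_R − (E_R + E_C)·θ·n_R/(θ·n_R + n_C)] = 0

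Here w is the uptake weight, n the counted days and E the expected recorded events in the risk (R) and control (C) windows. With zero lag θ = 1.000. With exponential lag and uptake uniform or peaked in October 2023:

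| Median lag | 21- and 28-day outcomes | 42-day outcomes |
|---|---|---|
| 3 days | about 1.03–1.2 | about 1.2–1.35 |
| 7 days | about 1.1–1.5 | about 1.5–1.8 |
| 14 days | 1.27–1.96 | 1.93–2.51 |

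The lag shape matters. If 7 days is the mean of an exponential, or the median of a lognormal with sigma 0.8, 42-day outcomes give 1.28–1.54 and 21-day outcomes 1.11–1.19.

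A 60-day run-out brings the scenarios in the table to 1.03 or below. Over the wider set (exponential mean or lognormal median up to 30 days) a 60-day run-out gives 1.00–1.12 and a 90-day run-out 1.00–1.05. Keeping only complete control windows, without a run-out, still leaves 1.09–1.51 for 42-day outcomes at lags of 7–14 days.

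**Step 4: the plan's signal rule.** With n events and equal windows, the risk-window count is binomial with p = RR/(1 + RR). With n = 30, a ratio above 3.0 needs at least 23 risk-window events (23/7 = 3.3; 22/8 = 2.75), and 23 also meets P < 0.01. The chance is 0.3% at RR 1, 4.4% at an induced RR of 1.5 and 16.7% at 2.0. With 200 events at 2.0 it is 0.4%.

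**The case against.** **Same-day extraction is not established.** Footnote a gives a planned start, with no finish date. Section 6 dates the final protocol 31 March 2024, and Section 10.3 allows the project to begin only after IRB approval or exemption. If that governed the interim extract, it would come at least 76 days after 15 January (16 + 29 + 31), and the null ratio would be at most 1.014 at a 14-day median lag. This stands as a limit: the fault is that the plan requires no run-out, and the documents do not show that none occurred. The end of interim person-time on 15 January is likewise inferred from footnote b, because the end of data collection is defined only for the final report (31 August 2025).

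**Readings that go too far.** A reader might infer that unfinished control windows are counted at full length. They are not; Section 9.2.5.1 truncates them, and only days up to the cut-off are over-counted relative to their claims. A reader might also test at a nominal 5% level with 200 cases and find rejection in 79–87% of studies (42-day outcomes, 7-day median lag). The plan does not act on that rule, gives no case count, and says in Section 9.9 that the interim may be underpowered. Nor is the whole study compromised: the SCRI is repeated in ORD. The last possible control day there is 31 March + 114 days = 23 July 2024, over a year before the dataset is due to be completely available.

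**What does not answer the point.** Daily claim processing (Section 9.4.1) shortens the lag but does not abolish it. Low power is imprecision, whereas this is a shift in one direction. The matter cannot be left to another document: Section 7 calls this the combined protocol and SAP, and Annex 1 lists no standalone documents.

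**Conclusion.** The point holds for the interim SCRI as written. Its direction needs only a non-zero lag and extraction at or close to the cut-off. Its size rests on assumed lag, uptake and constant incidence: a few percent for short windows and short lags, and roughly 1.5–1.8 for 42-day outcomes at a 7-day median lag. Seasonal change in event rates could add to it or offset it. False signals under the plan's own rule would be uncommon unless lags are long, although Section 9.3.2 also permits retrieval for estimates approaching the threshold. The final ORD SCRI is largely unaffected. The plan should be corrected and the interim estimates qualified; the study's final conclusions are not undermined on this ground.

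**What to change.** In Section 6 and Section 9.2.5.1, define the interim person-time cut-off and the interim extraction date separately. Either place a run-out between them (60–90 days fits within the 167 days to 30 June 2024), or end interim person-time at an earlier date by which claims are shown to be complete. Restricting to complete control windows is not a substitute.

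Because the interim milestone has passed:

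- state the date on which the interim data were actually extracted;
- add claim-lag bias, with its upward direction, to Section 9.9;
- in the final report, show an ORD SCRI restricted to person-time through 15 January 2024 beside the interim estimates, and say that the matured ORD result supersedes them.

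ORD is a different database, so a difference between the two would not isolate lag. Re-running the pre-adjudicated source is not proposed: it would need a new extract, and Section 9.4.1 says that database captures only up to three years of prior data.

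The cost is a few sentences and one extra run on data already extracted for the final report.
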